## 6.2 Subject Characteristics

#### 6.2.1 Subject Disposition

The number of subjects who have been screened, screen failed, and randomized will be summarized by treatment group and overall. The number of subjects who discontinue study treatment or study follow-up will be summarized by treatment group, along with the reasons for discontinuation. The number of subjects in each analysis population will be summarized by treatment group.

Listings of the subject disposition and enrollment eligibility, analysis populations, and treatment assignment will be provided.

## 6.2.2 Protocol Deviations

Protocol deviations will be presented in a data listing, by treatment group for the Safety population. Protocol deviations will be captured through data review and site monitoring.

## 6.2.3 Background and Demographic Characteristics

Demographic information (e.g., age, sex, race, height, weight, body mass index [BMI], and ethnicity) will be summarized for the ITT population, by treatment group and overall with summary statistics for continuous/categorical variables.

## 6.2.4 Treatment Exposure and Compliance

## 6.2.4.1 eDiary Exposure

Exposure will be collected in the eDiary, where for Days 1-7 subjects will be asked how many pills they take each day. A listing will be provided, for the ITT population, to report treatment exposure for Days 1-7, where subjects are instructed to take 1 or more pills a day.

## 6.2.4.2 Overall Exposure and Compliance

Duration of exposure and compliance will be summarized for the ITT population by treatment group and overall for the active treatment groups using descriptive statistics.

Duration of exposure will be summarized as time in days from first treatment to last dose, calculated as last dose date minus first dose date plus 1 day.

Compliance will be summarized using data from the electronic case report form (eCRF). A percent compliance value (shown derived below) will be calculated and listed for each subject.

Number of pills taken Expected number of pills taken \* 100

## 6.2.5 Prior and Concomitant Medications and Therapies

The start and stop of each medication will be recorded by calendar date. "Prior medications" are defined as medications that have been discontinued prior to the date of first dose of study drug. "Concomitant medications" are defined as medications taken any day from the first dose of study drug until the last dose of study drug, regardless of whether the medication was initiated prior to the first dose of study drug.

The counts and percentages of subjects who took prior and concomitant medications will be summarized on the safety population, by treatment group and overall. Prior and concomitant medications will also be presented in subject data listings.

For partial start or stop dates, the following considerations and imputations will be performed.

- For a partial or missing start date where the stop date is recorded in full and is before the date of initial study treatment, it will be considered a prior medication. If the stop date is after the date of initial study treatment, it will be considered a concomitant medication.
- For a partial or missing stop date where the start date is recorded in full and the start date is after the initial study treatment date, it will be considered a concomitant medication.
- For instances where a medication has a partial stop date and a partial start date, the month and year of the stop date will be used to assess whether the medication is prior or concomitant. For instance, if month and year exist for the stop date, this data will be compared with the date of initial study treatment and if the month or year show evidence of being after this date or on the same date (same month/year), the medication will be considered concomitant.
- For medications where both the start and stop dates are missing, these medications will be considered concomitant.

The prior and concomitant medications taken during the study will be summarized using number of subjects (n) and percentage (%) in the safety population. All prior and concomitant medications will be coded using the WHODDE, version September 2015 or later, and then further coded against the

Anatomic Therapeutic Chemical (ATC) classification. Prior and concomitant medication data will be presented by ATC Level 2 and preferred term and will be presented by treatment group.

## 6.2.6 Medical Histories

General medical history and surgical history data will be captured during the screening period, both at screening and Day 1. A listing of medical and surgical history data will be provided on the Safety population.

## 6.3 Efficacy Analyses

## 6.3.1 Analyses of all hot flash frequency and severity endpoints both Primary and Secondary

The following conventions apply to all analyses of hot flash frequency and severity data:

Population: The EE population (efficacy evaluable) population will be the population of interest in the primary and all secondary endpoint analyses. The EEIA (efficacy evaluable interim analysis) population will be the population of interest for the analysis conducted at Week 6. The ITT population will be used in the sensitivity analyses to verify that the findings remain consistent.

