### **9.3 Efficacy Analyses**

The primary efficacy analyses will be among the EE (EEIA) population. The comparison of percentage change in frequency from baseline to Week 6 between the placebo arm and each

of the 10 mg and 50 mg dose arms will be of primary interest in Stage 1. In Stage 2, the comparison of percentage change in frequency from baseline to Week 6 between the placebo arm and the 100 mg dose arm will be of primary interest.

Subjects will record events of hot flashes (frequency and severity) utilizing an application on an electronic device (i.e. smartphone). An example of the specific questions asked and definitions of severity are included in [Appendix C](#)

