#### 4.8 eDiary Assessment

Subjects will be provided with an Electronic Diary (eDiary) at the Screening Visit to collect data for hot flashes during screening. If enrolled, they will continue to use the eDiary to collect hot flash information for each hot flash through Day 84/Early Termination. All subjects should be instructed to return the eDiary to the study site. Subjects must be educated to record the hot flash assessments in the eDiary in real time.

The table in Appendix 9.1 outlines the timing of assessments to be recorded throughout the study in the eDiary. Appendix 9.3 further elaborates on the hot flash assessment and provides a list of the three severity levels of hot flashes along with a description of the symptoms associated with each level.

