## 5. ANALYSIS POPULATIONS

The subjects will be over the age of 18 and will have moderate to severe hot flashes, defined as a minimum of 4 moderate to severe hot flashes per day or 12 per week at baseline. The 4populations are as follows:

Intent-to-Treat (ITT) population:	All enrolled subjects who have taken at least 1 dose of study drug.
Efficacy Evaluable (EE) population:	All subjects in the ITT population who have analyzable baseline data and 12 weeks of hot flash data. Subjects must also be at least 80% compliant with taking study drug with no major protocol deviations, including no major inclusion/exclusion deviations.

Efficacy Evaluable (EEIA) population for IA:	All subjects in the ITT population who have analyzable baseline data and 6 weeks of hot flash data. Subjects must also be at least 80% compliant with taking study drug with no major protocol deviations, including no major inclusion/exclusion deviations.
Safety population:	All subjects who receive at least 1 dose of study drug. The safety analyses will be conducted on this population. This population is the same as the ITT population.

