## Data Handling

Baseline week will be determined from the second week of the first two weeks of hot flash eDiary that were recorded; if a patient qualified for study entry by number of hot flashes during the second week of screening, then data from that week will be used as their baseline. However, if a patient did not qualify for study entry based on the number of hot flashes during that second week then data from the screening week that was used to qualify the patient will be used as their baseline instead. A week's data collection will be considered the 6 days prior to plus the day of week's data. For example, Week 6 data will include the data collected for the 7 days from Day 36 through Day 42, inclusive. For a subject's data to be considered non-missing for a given week the subject must have recorded at least 4 days of data during the respective week. For subjects who report at least 4 days of data during a week, the weekly frequency of moderate and severe hot flashes will be the sum across those days of the number of moderate to severe hot flashes. The severity level reported for each of the reported hot flashes will be calculated as follows. Baseline severity level will be the number of severe hot flashes reported times 3 + the number of moderate hot flashes reported times 2 then divided by the number of moderate and severe hot flashes reported. Post-baseline weeks will have their severity level calculated as above but with the addition of reported mild hot flashes so the post-baseline severity for a given week level will be the number of severe hot flashes reported times 3 + the number of moderate hot flashes reported times 2 + the number of mild hot flashes reported times 1 then divided by the number of mild, moderate and severe hot flashes reported. The percentage change from baseline of the frequency of moderate and severe hot flashes will be the number of moderate to severe hot flashes reported for the given week minus the number reported at baseline then divided by the number reported at baseline and converted to a percentage by multiplying by 100. The percentage change from baseline of the severity of moderate and severe hot flashes will be the calculated severity score reported for the given week minus the severity score at baseline then divided by the severity level reported at baseline and converted to a percentage by multiplying by 100.

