# 6.3.1.1.2 Additional frequency analyses – sensitivity analyses among the ITT population Sensitivity analyses will also be conducted on the ITT population as described above.

## 6.3.1.1.1 Additional frequency analyses – sensitivity analyses including all severity levels

Sensitivity analyses on the percentage change in frequency of hot flashes from baseline to Week 6 will be conducted where a subject's frequency of hot flashes for a given week will include any hot flash designated as mild, moderate, or severe. This will be conducted among subjects in the EEIA population and among those in the ITT population.

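### The Week 6 primary test uses a set fixed largely after randomisation (EEIA); ITT is only a sensitivity set, and the SAP is unclear whether it is run at the interim

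*SAP*

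**What the plan says.** Protocol 9.3 sets the primary analysis population: "The primary efficacy analyses will be among the EE (EEIA) population". Protocol 9.3.1.1 repeats this for Week 6 frequency and times the primary analysis for when the last patient reaches Day 42. SAP 6.3.1 makes two statements. One is "The EE population (efficacy evaluable) population will be the population of interest in the primary and all secondary endpoint analyses"; the other is "The EEIA (efficacy evaluable interim analysis) population will be the population of interest for the analysis conducted at Week 6".

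EEIA is defined in SAP 5 as "All subjects in the ITT population who have analyzable baseline data and 6 weeks of hot flash data", with the further conditions of at least 80% drug compliance and no major protocol deviations. EE is the same with 12 weeks of data. ITT is every enrolled subject who took at least one dose.

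ITT has a secondary role: "The ITT population will be used in the sensitivity analyses to verify that the findings remain consistent". SAP 6.3.1.1.2 repeats it: "Sensitivity analyses will also be conducted on the ITT population as described above".

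Two data rules decide who falls outside EEIA. For a week to count as non-missing, "the subject must have recorded at least 4 days of data during the respective week". Diary collection has a natural end: once enrolled, "they will continue to use the eDiary to collect hot flash information for each hot flash through Day 84/Early Termination".

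SAP 6.7 makes three statements about the interim: the MMRM is run on both ITT and EEIA; the associated sensitivity analyses are not run; and all interim analyses are on EEIA.

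**The concern.** Apart from baseline data and eligibility, the EEIA conditions are known only after randomisation. A man who leaves before Week 6 is complete will generally lack 6 weeks of data. One who leaves in its last days may still qualify, because four diary days make a week. A man outside EEIA takes all his recorded weeks with him. Protocol 9.3.1.1 presents the MMRM as a way to use the preceding weeks, yet the early weeks of men without later ones are discarded.

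Exit can also be selective. Related Grade 3 or worse toxicity leads to discontinuation (Protocol 8.11) and could depend on arm. Need for a prohibited medicine, several of which are hot-flash treatments, leads to withdrawal (Protocol 8.15 and 8.16) and could depend on response. Neither alone inflates the error much; the two together can.

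Under SAP 6.7 a significant Stage 1 result lets the sponsor choose not to start Stage 2, and otherwise Stage 2 follows, with safety also considered. The SAP does not make clear whether an ITT result will be available as a check at that point. Nor does it say whether EE or EEIA gives the primary Week 6 result in the final report.

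**Working it through.** **The plan's own figure.** Protocol 9.1 gives 30 per arm for one-sided alpha 0.10, power 0.90, a 40% lower frequency, and variance equal to the active-arm mean. With placebo mean m, n = 2 × 0.6m × (1.2816 + 1.2816)² / (0.4m)² = 49.27/m. The documents do not give m, so 30 can be neither confirmed nor refuted. It implies a standardised effect of √(2 × 6.569/30) = 0.662. No dropout allowance is stated and leavers are not replaced. If EEIA keeps 27 or 24 men per arm, power for a simple two-sample comparison at one-sided 0.10 falls from 0.90 to 0.875 or 0.844.

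**Assumptions for the comparison of sets.** Six weekly percentage-change values, SD 40 points, 30 per arm, no drug effect, exit after Week 3. True correlation was compound symmetry (CS) at 0.4, 0.6 or 0.8, or AR(1) at 0.8. The SAP mean model (treatment, linear week, interaction) was fitted by REML, with CS or AR(1) chosen by AIC, and the Week 6 contrast tested one-sided at 0.10. EEIA was taken as six-week completers; in ITT, leavers contribute Weeks 1-3. There were 1,500 runs per cell (Monte Carlo SE about 0.005-0.013). With no exit the error was 0.092-0.095.

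**Precision.** Mean SE with 20% random loss in both arms:

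| Correlation | EEIA | ITT | Variance ratio |
|---|---|---|---|
| CS 0.4 | 9.78 | 9.39 | (9.78/9.39)² = 1.08 |
| CS 0.6 | 10.42 | 9.75 | 1.14 |
| CS 0.8 | 10.95 | 9.99 | 1.20 |
| AR(1) 0.8 | 11.45 | 10.98 | 1.09 |

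At 10% loss the EEIA variance is 4-9% larger.

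**Type I error at 20% active-arm loss, EEIA / ITT.** Graded exit is logistic in the Week 3 value, with the stated slope per SD.

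| Exit pattern | CS 0.4 | CS 0.6 | CS 0.8 | AR(1) 0.8 |
|---|---|---|---|---|
| Graded 1.0, active only | 0.154 / 0.085 | 0.211 / 0.108 | 0.233 / 0.109 | 0.171 / 0.093 |
| Graded 1.5, active only | 0.205 / 0.098 | 0.257 / 0.097 | 0.284 / 0.105 | 0.233 / 0.110 |
| Graded 1.5, 20% active and 10% placebo | 0.141 / 0.101 | 0.149 / 0.087 | 0.175 / 0.104 | 0.146 / 0.097 |
| Exactly the poorest, active only | 0.293 / 0.107 | 0.375 / 0.109 | 0.482 / 0.101 | 0.286 / 0.099 |

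**Other patterns.**

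- Graded, active only, 10% loss: EEIA 0.14-0.17, shifted 2.0-3.8 points toward the drug. At 20% the shift is 2.6-7.2 points.
- Exactly the poorest, active only, 10% loss: EEIA 0.17-0.27.
- Exit unrelated to response, in one arm or both: EEIA 0.09-0.11.
- Graded exit equal in both arms: EEIA 0.10-0.12. A separate run gave up to about 0.15 if exactly the poorest leave both arms.
- Graded, placebo only: EEIA 0.04-0.06 at 10% and 0.02-0.04 at 20%, against the drug.
- ITT MMRM across the patterns run, from the precision comparison to this point: 0.08-0.11.
- Graded active-only exit driven by the unseen Week 6 value: EEIA 0.19-0.21 at 10% and 0.28-0.34 at 20%; ITT MMRM 0.12-0.16 and 0.12-0.25.

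**Second set-up.** Here the covariance is known, active-arm leavers come from the worst responders at Week 2, placebo loss is random, loss is 10-30% active and 10-20% placebo, and correlation is 0.5 or 0.8. EEIA error is 0.16-0.29, against 0.09-0.11 using all rows.

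**Not modelled.** Unstructured covariance, the compliance and deviation exclusions, the slope tests, and the Hochberg step.

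**The case against.** The strongest reply is that the plan already contains the remedy. ITT analysis of the primary endpoint is pre-specified, and one sentence in SAP 6.7 expressly puts the ITT MMRM in the interim. The sensitivity analyses it excludes could be only those that count mild hot flashes. That reading is possible, but SAP 6.3.1 and 6.3.1.1.2 themselves class ITT as sensitivity, and SAP 6.7 then confines all interim analyses to EEIA. The ambiguity remains.

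This is a Phase 2 study at one-sided 0.10, with an evaluable set declared in advance and only a reserved right not to start Stage 2. That limits the severity and does not remove the point.

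The inflation rests on assumed inputs and needs exit to depend on arm and response together; no passage shows that this will happen. This stands. The worst-case row is a bound, not a forecast. At 10% graded loss the shift is well under one SE, but in a one-sided 0.10 test that still matters. With a round SE of 10.5, Φ(−(1.2816 − 2.0/10.5)) = 0.14 and Φ(−(1.2816 − 3.8/10.5)) = 0.18.

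The simulated test is a single mean comparison. Stage 1 success is Hochberg over four tests, so these figures are not the error rate of the Stage 2 decision. This also stands; they compare the two analysis sets.

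The ITT MMRM is not a full cure when exit depends on unseen values. The SAP's ITT is itself a dosed set, although SAP 4.2 randomises 2 to 5 days before Day 1. Both points are right. The first is why a further sensitivity analysis is needed.

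**Conclusion.** The concern holds. The text puts the Week 6 primary comparison on a set selected largely after randomisation, makes ITT a sensitivity set, and contradicts itself on whether ITT is run at the interim. None of that depends on a simulation.

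Loss of information follows from any early exit: roughly 9-20% more variance at 20% random loss, under the assumed SD, correlations and exit time. Bias is conditional and can go either way. Under the same assumptions, EEIA error is near nominal when exit is unrelated to response. It is 0.15-0.28 when 20% of the active arm leaves with poorer responders over-represented, and below nominal when that happens on placebo only. The ITT MMRM stays at 0.08-0.11 in these cases and corrects only partly for exit driven by unseen values. The sponsor should make the change. Confidence is high in the reading of the text; the size of any inflation depends on exit patterns that the documents do not describe.

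**What to change.** - In SAP 6.3.1 and Protocol 9.3 and 9.3.1.1, make the MMRM on ITT (all dosed subjects, every available week) the primary analysis of Week 6 frequency, including at the Day 42 analysis. Keep EEIA and EE as supportive sets.
- In SAP 6.7, reconcile the three sentences so that the ITT MMRM is run at the interim.
- State which analysis is the primary Week 6 result in the final report.
- Add one missing-not-at-random sensitivity analysis, for example placebo-based or tipping-point imputation after exit.
- Minor wording: define what counts as 6 weeks of hot flash data, state the period over which 80% compliance is measured, and replace the undefined PP set in Protocol 9.3.2.1.

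The cost is wording in both documents and one added analysis, since the ITT analysis is already planned. The downside is some dilution of the effect by non-compliant men, which the supportive EEIA analysis would show.

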## Data Handling

Baseline week will be determined from the second week of the first two weeks of hot flash eDiary that were recorded; if a patient qualified for study entry by number of hot flashes during the second week of screening, then data from that week will be used as their baseline. However, if a patient did not qualify for study entry based on the number of hot flashes during that second week then data from the screening week that was used to qualify the patient will be used as their baseline instead. A week's data collection will be considered the 6 days prior to plus the day of week's data. For example, Week 6 data will include the data collected for the 7 days from Day 36 through Day 42, inclusive. For a subject's data to be considered non-missing for a given week the subject must have recorded at least 4 days of data during the respective week. For subjects who report at least 4 days of data during a week, the weekly frequency of moderate and severe hot flashes will be the sum across those days of the number of moderate to severe hot flashes. The severity level reported for each of the reported hot flashes will be calculated as follows. Baseline severity level will be the number of severe hot flashes reported times 3 + the number of moderate hot flashes reported times 2 then divided by the number of moderate and severe hot flashes reported. Post-baseline weeks will have their severity level calculated as above but with the addition of reported mild hot flashes so the post-baseline severity for a given week level will be the number of severe hot flashes reported times 3 + the number of moderate hot flashes reported times 2 + the number of mild hot flashes reported times 1 then divided by the number of mild, moderate and severe hot flashes reported. The percentage change from baseline of the frequency of moderate and severe hot flashes will be the number of moderate to severe hot flashes reported for the given week minus the number reported at baseline then divided by the number reported at baseline and converted to a percentage by multiplying by 100. The percentage change from baseline of the severity of moderate and severe hot flashes will be the calculated severity score reported for the given week minus the severity score at baseline then divided by the severity level reported at baseline and converted to a percentage by multiplying by 100.

